4.4 Subject Recruitment and Screening

32 subjects will be recruited and we expect to recruit subjects between the ages of 18 and 90 with multiple comorbidities. Subjects will be recruited from the investigator or sub-investigator clinical practices. No advertisement will be conducted. Screening requirements include serum measurement of creatinine, bicarbonate, and in patients with known hepatic dysfunction, aspartate aminotransferase, alanine aminotransferase and alkaline phosphatase should be measured.

4.5 Early Withdrawal of Subjects

4.5.1 When and How to Withdraw Subjects

Withdrawal criteria and procedures specifying when and how to withdraw subjects from the trial:

Patients can withdraw at any time during the study if they no longer want to participate in the trial. If withdrawal occurs no further metformin administration will occur and patients will be required to return remaining metformin tablets which will be logged in to medication administration records and destroyed. If a subject withdraws consent to participate in the study, permission will be sought to use data pertaining to the subject in the analysis as far as they participate and they will be removed from subsequent analyses. We will also attempt to obtain consent from the subject to record survival and progression for one year after enrollment. It is a high priority to try to obtain survival and progression free survival data on all subjects.

Description of when a subject's participation in the trial may be discontinued:

Specific reasons for discontinuing a subject from this study are:

1. Voluntary discontinuation by the subject who is at any time free to discontinue their participation in the study, without prejudice to further treatment.
2. Safety reasons as judged by the investigator.
3. Severe non-compliance to the protocol as judged by the investigator.
4. Incorrect enrollment of the subject.
5. Subject lost to follow-up
6. Death

4.5.2 Data Collection and Follow-up for Withdrawn Subjects

Survival data will be collected for subjects that withdraw prematurely as well as progression of disease information. If a subject withdraws consent to participate in the study, permission will be sought permission will be sought to use data pertaining to the

subject in the analysis as far as they participate and they will be removed from subsequent analyses. Consent will also be sought from the subject to record survival and progression for one year after enrollment. It is a high priority to try to obtain survival and progression free survival data on all subjects lost to follow-up. Subjects will be called by phone at least on three occasions, phone calls at least twice will be carried out to the next-of-kin and certified letters will be sent twice. If follow-up is not obtained after the previously listed attempts have been carried out the subject will be considered lost to follow-up.

5.0 STUDY DRUG/THERAPY

5.1 Description

Metformin is a biguanide drug currently approved for the treatment of type 2 diabetes mellitus by the FDA. It is currently being investigated in multiple cancer treatment trials.

5.2 Treatment Regimen

Metformin is the therapeutic agent in the protocol. The initial starting dose will be 500mg orally daily for 3 days which then will be increased to 500 mg twice daily and, if tolerated, further increased to 1000mg twice daily after day 6. Patients will maintain 1000 mg twice a day dosing until 2 weeks after completing their radiation. This dose schedule has been shown to be well tolerated.

See Section 5.11 for information on the placebo.

5.3 Risks

Summary of known and potential risks and benefits, if any, to subjects:

Metformin's most serious toxicity is lactic acidosis, occurring in three of 100,000 patient-years of use. Risk is significantly reduced when metformin use is avoided in those patients with hepatic, cardiac, or renal compromise and in those age 80 years or older. However, metformin's risk of lactic acidosis may be overstated since the recent evaluation of metformin associated lactic acidosis cases from 347 trials showed that the risk of lactic acidosis with metformin was not significantly increased compared with other antihyperglycemic agents²⁷. Minor gastrointestinal upset is the most common toxicity, leading to cessation of therapy in less than 5% of individuals. Metformin does not cause hypoglycemia. The possible societal benefits are large since this will allow us to learn about the pharmacodynamic effects of metformin in RAI, allowing for radioprotection against myelosuppression, xerostomia, and other sequelae of radioactive iodine treatment, as well as metformin's tolerability and safety profile in a cancer population. The study is designed to assess as the primary end-point the effects of metformin on radiation-induced bone-marrow suppression with short term administration and not to assess if metformin improves outcomes in cancer and hence it is unlikely to improve the clinical outcome of the subjects enrolled in this study.

Rules for dose modification: Toxicity monitoring, dose modification and treatment of complications:

Particular attention will be paid in the first three days of treatment. Patients will take 500 mg/day for 3 days. From day 4, 500 mg twice daily and then in 3 days dose escalation to 1000 mg twice daily will be achieved. This will be continued for two weeks following RAI treatment. A phone call on the day of each dose escalation will be made in order to evaluate the tolerability of the drug and also weekly thereafter. Patients will be instructed to contact the clinical investigators should any toxicity occur during the study¹⁹.

Metformin will be started the following day if CAT scan with intravenous contrast is administered to decrease risk of lactic acidosis. This further mitigates this risk. This approach is more stringent than the most recent recommendation of the American College of Radiology which does not recommend holding metformin in the absence of comorbidities (renal insufficiency, liver dysfunction, alcohol abuse, cardiac failure, myocardial or peripheral muscle ischemia, sepsis or severe infection) which are exclusion criteria for this clinical trial³¹. CAT scan is not used routinely in patients with thyroid cancer as it is desirable to avoid iodinated contrast.

Toxicity will be evaluated using the most recent version (version 4) of the NCI toxicity criteria, i.e. the NCI Common Terminology Criteria for Adverse Events (CTCAE) version 4.0. The CTCAE provides descriptive terminology and a grading scale for each adverse event listed. A copy of the CTCAE can be found at <http://ctep.cancer.gov>.

Grade 1 toxicity: Patient will be maintained on full dose.

Grade 2 toxicity: Dose will be reduced by 50% until grade 1 or lower. If symptoms are not resolved within 3 days the treatment will be discontinued definitively.

Grade 3 toxicity (probably or definitely drug related): Treatment will be interrupted and toxicity reassessed daily. If toxicity improves to grade 2, dose will be reduced by 50%.

Grade 4 toxicity (probably or definitely drug related): Treatment will be discontinued definitively.

In case of grade 1 or 2 diarrhea (the most frequent side effect) a concomitant administration of loperamide will be provided.

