There are currently multiple ongoing studies using doses from 500 mg twice daily up to 2500 mg per day in the treatment arms. There are also studies using the extended release form for a dose of 1500 mg daily. We have chosen our starting dose and escalation regimen to minimize side effects. The chosen standing dose is based on metformin's therapeutic range (minimal therapeutic dose in diabetic patients is 1500-2000 mg a day)^{28, 29}. The time of planned exposure to metformin will be 3 weeks. We will allow a window of an additional 2 weeks in the event that there are delays in the treatment scheduling but no patients will receive metformin for more than 35 days.

Rules for dose modification: Toxicity monitoring, dose modification and treatment of complications:

Particular attention will be paid in the first three days of treatment. Patients will take 500 mg/day for 3 days. From day 4, 500 mg twice daily and then in 3 days dose escalation to 1000 mg twice daily will be achieved. A phone call on the day of each dose escalation will be made in order to evaluate the tolerability of the drug and also weekly thereafter. Patients will be instructed to contact the clinical investigators should any side effects occur during the study¹⁹.

In the event that an iodinated IV contrast dye load for CT scanning is required at some point during the metformin treatment period, the drug will be stopped the day before IV dye administration, as is the standard practice among patients taking metformin. However, IV contrast dye generally precludes treatment with RAI as the iodinated contrast competes with RAI and thus limits its effect. Therefore, it is extremely unlikely that any patient will be receiving iodinated contrast at the time of the study. Furthermore, this measure is generally considered to be conservative as the risk of lactic acidosis in patients taking metformin has not been shown to be higher than that of the general population after IV contrast dye in recent literature. Nevertheless, this measure is in compliance with current American College of Radiology guidelines^{30, 31}. Metformin will be resumed the day after RAI treatment completion at the last dose the subject was receiving prior to being held and if escalation was planned as previously described.

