2.0 STUDY OBJECTIVES

1. To estimate the capacity of metformin to mitigate radioactive iodine therapy-induced myelosuppression as assessed by CBC
2. To assess the capacity of metformin to mitigate known side effects of radioactive iodine therapy including xerostomia, xerophthalmia, and dysgeusia as assessed by standardized questionnaire
3. To analyze changes in serum and salivary exosome profiles following a trial of metformin administration in patients receiving radioactive iodine treatment

2.1 Primary Objective:

We have chosen complete blood count (CBC) as our primary endpoint and serum and salivary exosome profiles as secondary endpoints. To evaluate if treatment with metformin inhibits RAI-induced myelosuppression and induces faster recovery of white blood cell count to baseline values, the blood counts will be compared in the pre- and post-treatment samples. Blood parameters will include hemoglobin, red blood-cell count, white blood-cell count, absolute neutrophil count, absolute lymphocyte count, and

Thomas
Jefferson
University

platelet count. Blood and salivary samples will be drawn before surgery, before and immediately after treatment with metformin and RAI, and every three months thereafter for one year.

All blood samples will be taken by a phlebotomist or trained personnel. A baseline blood sample, consisting of two tubes of 1 cc of whole blood each, will be drawn before thyroidectomy as part of standard procedure at patients' pre-operative testing appointment. Patients will recover for a period of 6-8 weeks and identical samples will be drawn within 72 hours of starting metformin. Then samples will be drawn within three days before and within three days after RAI treatment, at the conclusion of metformin treatment, and every three months thereafter for one year. Blood parameters will include hemoglobin, red blood-cell count (RBC), white blood-cell count (WBC), absolute neutrophil count (ANC), absolute lymphocyte count (ALC), and platelet count. Assays will also be conducted on samples to assess metformin-induced changes in serum and salivary cytokines and growth factors, erythrocyte sedimentation rate (ESR), exosome evaluation, and metabolomics profile. 5 cc samples of patient saliva will be collected in specimen cups.

2.2 Secondary Objective:

- Assess safety and tolerability of metformin treatment in subjects undergoing RAI treatment for differentiated thyroid cancer

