3.0 STUDY DESIGN

3.1 General Design

Type of trial: Pilot Efficacy trial

Planned accrual period: 48 months

Planned follow-up period: 12 months

Planned enrollment: Total of 32 patients

Schema of the trial design, procedures, and stages:

Patients with a diagnosis of well-differentiated thyroid cancer who have undergone tumor resection and have indications for RAI treatment that meet our inclusion and exclusion criteria will be offered participation in this clinical trial. Patients who present to TJUH with a known diagnosis of differentiated thyroid cancer who plan to undergo surgical resection followed by radioactive iodine will be offered enrollment in the trial at the time of surgical scheduling. Patients who undergo lobectomy for atypia of undetermined significance/follicular lesion of undetermined significance or follicular neoplasm/suspicious for follicular neoplasm who are subsequently found to a malignancy will be offered enrollment at their first follow-up visit. After informed consent is signed and study subjects are randomized 1:1 to take metformin or placebo, patients will be administered metformin with dose escalation as tolerated until time of RAI treatment. There is no dose escalation for patients randomized to the placebo arm. Pre-operative and pre-RAI treatment CBC with differential will be compared to post-RAI treatment lab values. Standardized surveys assessing symptoms of xerostomia, sialadenitis, xerophthalmia and dysgeusia will be completed.

Participants' Follow-up: Participants' will have blood and saliva samples drawn post-op before metformin administration, before and immediately following RAI treatment, after metformin, and then every three months for 12 months. They will complete surveys at each post-op visit, and their medical records will be reviewed every 3 months for 12 months to assess for symptoms of myelosuppression, xerostomia, xerophthalmia, and dysgeusia. This will allow us to assess the radioprotective effects of metformin post-RAI treatment.

Purpose of the study: To estimate the radioprotective effect of metformin in subjects with differentiated thyroid cancer by evaluating both the ability of metformin to mitigate known side effects of radioactive iodine therapy as well as alter the exosome profile in the serum.

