5.9 Blinding of Study Drug

The bottle will be non-descript and contain either metformin or placebo depending on randomization. Patient will be blinded to which pill (metformin or placebo) they will receive. Pill bottle distribution will be completed by the research coordinator who will not be blinded. Principal investigator and care providers making assessments will not be blinded.

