8.2 Recording of Adverse Events

At each contact with the subject, the investigator will seek information on adverse events by specific questioning and, as appropriate, by examination. Information on all adverse events will be recorded immediately in the source document, and also in the appropriate adverse event module of the case report form (CRF). All clearly related signs, symptoms, and abnormal diagnostic procedures results should be recorded in the source document, though should be grouped under one diagnosis.

All adverse events occurring during the study period will be recorded.

The clinical course of each event will be followed until resolution, stabilization, or until it has been determined that the study treatment or participation is not the cause. Serious adverse events that are still ongoing at the end of the study period will be followed up to determine the final outcome. Any serious adverse event that occurs after the study period and is considered to be possibly related to the study treatment or study participation will be recorded and reported immediately.

8.3 Unblinding Procedures:

At the completion of the accrual period subjects will remain blinded until after the primary and secondary endpoints have been collected. Once study is complete, PI will unblind patients to their randomization upon request.

8.4 Stopping Rules:

Grade 4 toxicity (probably or definitely drug related): Treatment will be discontinued definitively.

Participants will be discontinued from study drug as per physician discretion

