Appendix A: Schedule of Events

Appendix A: Schedule of Events

Study Procedures	Screening	Visit 1	Visit 2 (End of Treatment) ^E	Follow-up ^F
Informed consent		X		
Inclusion/Exclusion Criteria	X	X		
Demographics, Medical history	X	X		
Physical examination, vitals, weight, blood pressure		X	X	
Randomization		X		
Quality of Life Questionnaires ^D		X	X	X ^C
Pathology Report histologic confirmation of disease if available	X			
Concomitant meds	X	X		
Toxicity and AE Assessment		X	X	X ^I
Pregnancy test ^J	X	X		

Treatment/ Intervention				
Metformin ^G		X	X	
Placebo ^H		X	X	
Radiation Treatment		X	X	
Correlative Studies				
Blood sample collection ^A		X	X	X ^C
Saliva sample collection ^B		X	X	X ^C

- A. Two 7ml purple top tubes are to be drawn at each time point and transported directly to [name] laboratory.
- B. 5ml of saliva is to be collected at each time point and transported directly to [name] laboratory.
- C. Blood samples, saliva samples, and quality of life questionnaires will be collected every 3 months for the first year post treatment. Collection will occur at participant's regularly scheduled appointments.
- D. Quality of life surveys include: EORTC QLQ – H&N35, modified Vanderbilt Head and Neck Cancer Symposium Survey, University of Washington Quality of Life Questionnaire, and Xerostomia Questionnaire (XQ). All questionnaires will be administered online via an IPad provided at the visit.
- E. Visit will occur following completion of metformin treatment for 2 weeks after RAI
- F. Patients will be seen at regularly scheduled appointments every 3 months for the 1st year post treatment. Participant's medical records will be reviewed every 3 months for 24 months
- G. The initial starting dose of metformin will be 500mg orally daily for 3 days which then will be increased to 500mg twice daily and, if tolerated, further increased to 1000mg twice daily after day 6. Patients will maintain 1000mg twice daily dosing until 2 weeks after completion of radiation. If patient must have CT scan with intravenous contrast, metformin will be held and participant will be instructed to start metformin the day following the scan.
- H. Placebo will be given as 500mg tablets twice daily with no dose escalation.
- I. Assessment for AEs will occur as a phone call performed 2 weeks after the last dose of metformin.

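### Tolerability calls are tied to dose escalation, which placebo lacks, so adverse events are sought more often on metformin in the first week, by staff who know the arm

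*Combined protocol and SAP*

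**What the plan says.** Section 2.2 lists as a secondary objective: "Assess safety and tolerability of metformin treatment in subjects undergoing RAI treatment for differentiated thyroid cancer". Placebo is the only concurrent comparator.

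The only timing given for safety calls during treatment is in sections 1.4 and 5.3. Section 1.4 has "A phone call on the day of each dose escalation will be made", and section 5.3 repeats the rule: "A phone call on the day of each dose escalation will be made in order to evaluate the tolerability of the drug". The end of that sentence adds weekly calls: "in order to evaluate the tolerability of the drug and also weekly thereafter". Metformin rises at about day 4 and about day 7.

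Placebo does not rise. Section 3.1: "There is no dose escalation for patients randomized to the placebo arm". Appendix A note H: "Placebo will be given as 500mg tablets twice daily with no dose escalation".

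Section 6.1 has call times arranged with participants at Visit 1, in a paragraph that covers both arms, but gives neither days nor frequency. Two later contacts, Visit 2 and the call two weeks after the last dose, appear in the schedule for all subjects, although notes E and I describe their timing in terms of metformin only.

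Section 8.2 links contacts to recorded events: "At each contact with the subject, the investigator will seek information on adverse events by specific questioning". On blinding, section 5.9 says: "Principal investigator and care providers making assessments will not be blinded". The coordinator is also unblinded; patients are blinded. No section describes an arm-unaware grader of severity or causality.

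**The concern.** The number of adverse events recorded depends partly on how often patients are asked. Here the asking is tied to an event in the dosing schedule that only one arm has. A site that follows the text calls a metformin patient at each dose step. For a placebo patient it finds no triggering day, and the weekly calls have nothing to follow. The missing calls fall in the first week, when a drug whose commonest toxicity is gastrointestinal is being stepped up.

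The unblinded assessment compounds this. Under section 5.3, action on grade 3 and 4 events depends on a judgement that they are probably or definitely drug related, and section 8.4 leaves discontinuation to physician discretion. Both judgements are made by people who may know the arm.

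At stake is the between-arm reading of safety and tolerability. With 16 patients per arm, a difference of one or two patients in a mild event is visible in a table and could be taken for a drug effect. Section 7 contains no adverse-event analysis that allows for unequal contact, and no analysis can recover events that were never asked about.

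**Working it through.** **Does placebo have an escalation day?** The bottle counts in sections 5.10.3 and 5.11 can be reproduced from the label schedules over 21 dosing days:

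- Metformin: 3 × 1 + 3 × 2 + 15 × 4 = 69 tablets, as stated.
- Placebo: 21 × 2 = 42 capsules, as stated.

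The placebo regimen is flat, so a call triggered by escalation cannot occur in that arm.

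**Contacts at which events are sought.** Visit 2 and the post-treatment call are counted in both arms. The days are approximate.

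| Arm and reading of the weekly clause | Calls on treatment | Visit 2 and later call | Total |
|---|---|---|---|
| Metformin | 4 (days 4, 7, 14, 21) | 2 | 6 |
| Placebo, weekly from first dose | 3 (days 7, 14, 21) | 2 | 5 |
| Placebo, weekly on the same later days as metformin | 2 (days 14, 21) | 2 | 4 |
| Placebo, no call triggered | 0 | 2 | 2 |

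**Effect on recorded events.** Suppose the true rates are equal and each contact independently elicits a given event with probability q. The chance that the event is recorded after c contacts is 1 − (1 − q)^c. The documents give no q; 0.3 and 0.5 are assumed.

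| c | q = 0.3 | q = 0.5 |
|---|---|---|
| 6 | 1 − 0.7^6 = 0.882 | 1 − 0.5^6 = 0.984 |
| 5 | 0.832 | 0.969 |
| 4 | 0.760 | 0.938 |
| 2 | 0.510 | 0.750 |

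Ratio of recorded events, metformin to placebo:

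- 6 against 5: 0.882 / 0.832 = 1.06; 0.984 / 0.969 = 1.02.
- 6 against 4: 0.882 / 0.760 = 1.16; 0.984 / 0.938 = 1.05.
- 6 against 2: 0.882 / 0.510 = 1.73; 0.984 / 0.750 = 1.31.

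**In patients.** If 30% truly had an event in each arm (also assumed), that is 16 × 0.30 = 4.8 patients per arm. At q = 0.3 with 6 against 2 contacts, the recorded numbers would be 4.8 × 0.882 = 4.2 and 4.8 × 0.510 = 2.4. At q = 0.5 with 6 against 5, they would both be about 4.7.

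**Direction.** For any q strictly between 0 and 1 the expression increases with c. Under equal true rates, more contacts therefore always mean more recorded events on metformin; only the amount depends on q. Arm-aware attribution is not quantified here.

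**The case against.** The strongest reply is that the plan does not reserve calls for metformin. The same sentence adds weekly calls, section 6.1 arranges calls with all participants, and all are told to report side effects. That stands. A reader might infer that escalation is the only trigger, or that placebo patients are not to be called. The text supports only that their call days are undefined and that the escalation-day calls have no counterpart. On the kindest reading the gap is one call.

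A second reply concerns size. A reader who leaves out the post-treatment call and gives placebo only Visit 2 would compare 5 contacts with 1 and reach 0.832 / 0.30 = 2.8 at q = 0.3. That count is not consistent: both contacts are worded around metformin, so if one is granted to placebo the other should be too. The blood and saliva collections within three days either side of radioactive iodine (section 2.1) may also be contacts. Adding two to each arm gives 8 against 4 in the widest case, and (1 − 0.7^8) / (1 − 0.7^4) = 0.942 / 0.760 = 1.24. The formula also treats contacts as independent, whereas Visit 2 can ask about the whole treatment period. These points shrink the effect without removing it.

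Third, a reader might extend the concern to efficacy. The documents do not support that. Blood counts are laboratory values. Xerostomia, xerophthalmia and dysgeusia are measured by self-completed questionnaires in patients the protocol blinds; record review is additional, and no chart-derived symptom endpoint is defined.

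Finally, unblinded assessors are a disclosed choice in a 32-patient pilot whose secondary analyses are primarily descriptive. That is fair. It is a reason to report the limit, not to leave the call schedule uneven.

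**Conclusion.** The point holds for the between-arm comparison of safety and tolerability. Followed as written, the plan questions the metformin arm more often in the first week, by one or two calls, and leaves the start of the weekly calls undefined for placebo. The bias is towards more recorded events on metformin. With 6 contacts against 5, 4 or 2, and an assumed 30% to 50% chance of elicitation per contact, the recorded ratio under equal true rates is about 1.02 to 1.7. That range rests on assumed values and on independent contacts; the direction does not depend on the value chosen within that model.

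A reader might conclude that the placebo arm is useless as a reference. That goes too far: patients are blinded, two scheduled contacts are shared, and a comparison with a stated caveat remains possible. This is a worthwhile and cheap correction, not a flaw that undermines the primary analysis. No sample-size figure changes.

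**What to change.** 1. In sections 1.4, 5.3 and 6.1 and in Appendix A, set the tolerability calls on the same study days, counted from first dose, in both arms. Keep every call already planned for metformin, so that only the trigger changes.
2. Use one scripted adverse-event checklist for all calls.
3. Word the post-treatment call, in section 6.1 and note I, as following the last dose of study drug.
4. State in section 5.9 and in the report that grading and attribution of events are not blinded, and that events labelled drug related are to be read with that limit.

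Blinding the investigator is not part of this change. The 69 tablets on a rising label and 42 capsules on a flat one would reveal the arm to anyone discussing doses or counting pills, and the coordinator accesses assignments under section 5.4.

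The cost is about two extra short calls for each of 16 placebo patients, or 32 calls. It would be one call each if weekly calls from first dose were already intended, and four each if none were. No dose or toxicity rule is touched and no staff are added.
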